After consent a participant ID will be assigned to subject. Demographics, medical history, height, and weight (**Demographics** and **Medical History** forms attached) will be recorded for each subject. Females will be given a urine-based pregnancy test onsite and result will be recorded. If inclusion criteria are met at this time, subject will be asked to schedule a visit at CAB with study nurses for a blood draw to perform CMP screening test. If CMP results are within normal range the subject will be enrolled and return to IFNH to receive study materials needed for participation in the study. If any CMP values are outside normal ranges subject will be advised that they do not fulfill all eligibility criteria, they will be given a copy of their CMP results, and if necessary, advised to see their primary care provider. All screened subjects will be documented on **Screening and Enrollment Log** (attached).

The final selection will be contingent upon the individuals meeting all eligibility criteria and deemed capable of complying with the study protocol.

Study Procedures

- Thirty subjects will be enrolled.
- **Food List:** Participants will maintain their usual diet except for a provided list of PAC-rich foods that they will be asked to abstain from for a 5-day wash-out period and during the 10-day intervention. The Food List is provided below. The goal is to have GP-SPI as the main/only source of PAC in the diet for the study period.
- **Wash-out and SPI (Day -5 through -1):** On day -5 (pre-baseline) before any supplementation, each subject will collect their fecal and urine sample. Each subject will then consume SPI twice a day (provided as pre-weighed packets of 20 g) during a 5-day wash-out period (days -5, -4, -3, -2, and -1). Subjects will be instructed to mix each packet of SPI in 250 mL of water or in a smoothie (recipe example below will be provided) using allowed foods as detailed in instructions and consume once in the morning before breakfast and once in the evening before dinner.

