- **Day 0:** On the following day each subject will collect their baseline (day 0) stool and urine samples (Fig. 1). They will visit the CAB building to have a blood sample (2 tablespoons or 30 mL) drawn by a study nurse. Blood will be used for CMP test and prepared serum will be aliquoted and stored at -80 °C until processing for marker analysis and metabolomics. Analysis of day 0 samples should help isolate any effects due to SPI alone from subsequent samples collected during GP-SPI intervention. On day 0 subjects will drop off urine and stool samples at IFNH and collect GP-SPI packets. On Day 0 participants will also take a break from consuming SPI and will start GP-SPI supplementation on morning of Day 1.
- **GP-SPI (Day 1 – 10):** Each subject will receive twenty pre-weighed 20 g packets of GP-SPI. On day 1 subjects will be instructed to mix each packet of GP-SPI in 250 mL of water or in smoothie (recipe example will be provided, please see below) using allowed foods as detailed in instructions and consume the GP-SPI mix once in the morning before breakfast and once in the evening before dinner for 10 consecutive days (Fig. 1).

- Subjects will be provided with a personal blender for smoothie preparation (value ~ \$25) that they can keep.
- **Digital food diary:** Participants will be asked to take photos of all their food and drink (except water) including the study supplements with their personal mobile computing device (e.g. smart phone, iPad, or similar). Participants will be required to download the free mobile app WhatsApp to send photos with a brief description of the food items. Photos and food description may also be sent to an email address that will be created for this study ([contact]). The food diary must be kept over the 5-day SPI and wash-out period, day 0 (break day), the 10-day GP-SPI intervention period, and up until the final blood draw on day 11 (17 days total).

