Stool Sample		1	2	1	1	1	1	2	
Urine Pregnancy	X								
SPI		Twice a day for 5 days	Break						
GP-SPI				Twice a day on days 1 - 10					
Food Diary		Daily up until blood draw on day 11							

Food List

To ensure that GP-SPI ingredient is the main source of PAC consumed, participants will be given the below list of PAC-rich foods that they will be asked to abstain from during the washout and study period as well as a list of allowed foods. The food list is based on published quantification of PACs in commonly consumed food items (21; 22). In addition, participants will be provided with the following example smoothie recipe.

Smoothie Recipe:

- 1 banana (or another fruit from the allowed list of foods)
- 175 - 200 mL water or milk (add more or less liquid depending on preference; may also use milk substitutes like soy, almond, or rice milk)
- 1 - 2 tablespoons ice cream or yogurt (may also use frozen yogurt or non-dairy ice cream)
- 1 packet of GP-SPI
- 1 or more cubes of ice - *optional*
- Combine ingredients and blend

Plant Foods to abstain from: Study participants should abstain from the below list of plant foods for 5 days before (i.e. washout period), during the 10-day study intervention period, and until after the final blood draw on day 11. These foods contain high levels of naturally occurring proanthocyanidin compounds, major bioactives in GP-SPI ingredient, and will interfere with interpretation of results.

- Berry fruits (green grapes, red grapes, blueberries, cranberries, choke berries, strawberries, black berries, bilberry, black currant, aronia, hawthorn, rosehip, sea buckthorn) and all berry products (i.e. juices, preserves, jams, etc.)
- Plums
- Apples

- Apricots
- Cherries

- Sorghum
- Barley
- Pinto beans
- Red kidney beans
- Small red beans
- Black-eyed peas

- Almonds
- Hazel nuts
- Pecans
- Pistachios
- Walnuts
- Peanuts with skins

- Olives
- Olive oil
- All vinegars

- Dark chocolate
- Milk chocolate

- Red wine
- White wine
- Green tea
- Black tea

- Cinnamon
- Curry powder

Plant Foods allowed during study period: The below list of plant foods have undetectable levels of proanthocyanidin compounds and may be freely consumed. Vegetables are not a significant source of proanthocyanidins and those not listed below may also be freely consumed.

- Cantaloupe
- Medjool dates
- Grape fruit
- Orange
- Tangerine
- Honeydew
- Watermelon
- Pineapple
- Figs
- Tomato

- Coffee

- Artichoke
- Asparagus
- Broccoli

- Broccoli Raab
- Cabbage

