- Carrot
- Celery
- Cucumber
- Eggplant
- Lettuce
- Onion
- Pepper
- Potato
- Radish
- Sweet potato
- Zucchini
- Beets

- Corn meal
- Tortilla chips
- Wheat
- Oats
- Rice
- Soybeans
- Navy beans
- Chick peas
- Macadamia nuts
- Pine nuts
- Brazil nuts

- White chocolate

- Basil
- Oregano
- Parsley
- Paprika
- Black pepper
- Mustard seeds
- Poppy seeds
- Garlic powder
- Ginger
- Onion powder
- Turmeric
- Cloves
- Chili powder

The following plant foods have low levels of proanthocyanidin compounds and may be consumed in moderation during the study period, meaning just 1 serving per day of any food from the list below.

- Pear (1 fruit)
- Nectarine (1 fruit)
- Cherries (10 cherries)
- Apricot (1 fruit)

- Kiwi (1 fruit)
- Avocado (1 fruit)
- Mango (1 fruit or 1 cup of sliced fruit)
- Banana (1 fruit)
- Persimmon (1 fruit)
- Pomegranate (1/4 cup kernels)

- Indian Squash (1 ounce or 28 g)
- Black beans (1 ounce or 28 g)
- Lentils (1 ounce or 28 g)

- Roasted peanuts (40 pieces = 1 ounce or 28 g)
- Peanut butter (1 tablespoon)
- Cashews (18 pieces = 1 ounce or 28 g)
- Chestnuts (8-10 kernels)

- Beer (1 can/bottle = 12 ounces)
- Apple juice (1 cup or 230 mL)
- Chocolate milk (1 cup or 230 mL)

A. Data Points

Data elements to be collected include: medical history, demographics, digital and written food diaries, adverse events, metabolomics data from blood and urine samples, microbiome data from fecal samples

B. Study Duration

It will take 2 years to complete this study. Each subject will participate for 17 days.

C. Endpoints

Primary endpoint:

- 1) Evaluate the effect of nutritional supplementation with GP-SPI on gut microbiota composition using 16S rRNA gene sequencing.

Secondary endpoints:

- 1) To evaluate the effect of GP-SPI on kidney and liver health/function (safety) via comprehensive metabolic panel (CMP).
- 2) Collect fecal, blood, and urine samples and store for a microbiome-wide association study (MWAS, funded by R01 AT010242-01).

Microbiome wide association study (MWAS)

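### Nothing keeps a participant's mixing vehicle (water or smoothie) the same from SPI to GP-SPI, and the example recipe does not fit the food list's daily limit on banana

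*Combined protocol and SAP*

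**What the plan says.** All of this is in section 1.3.

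- **SPI run-in (days -5 to -1).** Two packets a day: "mix each packet of SPI in 250 mL of water or in a smoothie (recipe example below will be provided".
- **GP-SPI (days 1 to 10).** The same two options: "On day 1 subjects will be instructed to mix each packet of GP-SPI in 250 mL of water or in smoothie". Participants are to "consume the GP-SPI mix once in the morning before breakfast and once in the evening before dinner for 10 consecutive days", which makes 20 packets.
- **Role of day 0.** The day 0 paragraph expects that sample to help separate effects of SPI alone from what follows under GP-SPI.
- **Smoothie recipe.** It is offered as an example, written per packet, and names only the GP-SPI packet. The fruit is "1 banana (or another fruit from the allowed list of foods"; the dairy item is "1 - 2 tablespoons ice cream or yogurt (may also use frozen yogurt or non-dairy ice cream"; for the liquid, participants "may also use milk substitutes like soy, almond, or rice milk".
- **Food list.** Banana is in the low-proanthocyanidin group, one fruit being a serving, with the rule "meaning just 1 serving per day of any food from the list below". Almonds are on the list of foods to avoid.
- **Diary.** Photographs cover the study supplements as well as food and drink.

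Neither the statistical paragraph of the microbiome-wide association study (section 1.3) nor section 6.1 mentions the vehicle.

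**The concern.** The inference rests on comparing each person before and after day 1. With no concurrent SPI group, that comparison isolates the grape polyphenols only to the extent that nothing else changes systematically when the product changes. The vehicle could. Someone who drinks SPI in water and GP-SPI in smoothies has followed the mixing instructions, yet has added fruit and dairy (or a substitute) up to twice a day, starting with GP-SPI.

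The planned analysis would not detect this. The rule for identifying strains that respond to the grape polyphenols drops only strains that also change under SPI alone. A strain responding to smoothie ingredients first taken on day 1 would not have changed during the run-in, so it would be kept. Section 1.5 says the pilot's data will feed the power calculation of the follow-up trial, so a biased change would carry forward.

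The recipe raises a different issue. The diet rules aim to make GP-SPI the main or only proanthocyanidin source. If the study's own recipe can take a participant over the study's own limit, staff cannot judge adherence consistently.

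**Working it through.** **1. Is the vehicle held constant?** The run-in and GP-SPI paragraphs offer the same options, and each stands alone. No sentence links the choice in one period to the choice in the other, or the morning packet to the evening packet, and none fixes the smoothie's contents.

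**2. Largest possible change for one person** (all SPI in water, all GP-SPI in smoothies as written):

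- smoothies: 0 in the run-in; 2 x 10 = 20 on days 1 to 10
- bananas: 20 x 1 = 20
- yogurt or ice cream: 20 x (1 to 2) = 20 to 40 tablespoons

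**3. Recipe against food list** (banana smoothie for both daily packets):

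| | As written | Limit |
|---|---|---|
| Per day | 2 x 1 = 2 | 1 |
| Days 1 to 10 | 2 x 10 = 20 | 10 |
| Run-in | 2 x 5 = 10 | 5 |

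The excess arises whether the one-serving rule applies to each food or to the group as a whole. One banana smoothie a day complies. If banana is used equally in both periods, the excess bears on adherence and background intake, not on the before-after contrast.

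**4. The plan's own figure.** Section 1.5 gives N = 16 and power 96.2% for a rise in *A. muciniphila* from 0.1% to 0.4% with SD 0.5%. The within-person correlation r is not stated. For baseline against day 10, with a two-sided paired test at 0.05:

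- SD of change = 0.5 x sqrt(2(1 - r))
- r = 0.82: SD 0.30; noncentrality (0.3/0.30) x sqrt(16) = 4.0; power 96.2%
- r = 0.5: SD 0.50; noncentrality 2.4; power 61.2%

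So the figure can be reproduced only by assuming r. Fixing the vehicle does not alter it.

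**5. Illustration of bias (assumed shifts, not figures from the documents).** Take no polyphenol effect and 24 completers (30 less 20%, section 4.3). Noncentrality = mean shift / SD of change x sqrt(24). The chance of a significant result, nominally 5%, is:

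| Assumed mean shift | Share of planned 0.3 | r = 0.5 | r = 0.82 |
|---|---|---|---|
| 0.03 | 10% | 5.9% | 7.6% |
| 0.075 | 25% | 10.9% | 21.7% |
| 0.15 | 50% | 29.1% | 65.0% |

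The SD of change is held fixed. A mixture of switchers and non-switchers would widen it and tend to lower these figures.

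**6. What those shifts require.** Mean shift = net share switching x shift per switcher. The net share is not in the documents; assume 10% to 40%, which is 2.4 to 9.6 of 24. Shift per switcher:

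- mean 0.03: 0.03/0.40 = 0.075 to 0.03/0.10 = 0.30
- mean 0.075: 0.1875 to 0.75
- mean 0.15: 0.375 to 1.5

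The last row of the table therefore needs every switcher to move by more than the whole planned effect of 0.3.

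**The case against.** The strongest reply is that the plan treats both periods alike. The options are identical, and the run-in paragraph promises the recipe for SPI too, although the recipe itself names only GP-SPI. Switches in both directions would mostly add noise; bias needs a net drift one way. A reader might infer that the plan ties a diet change to GP-SPI. It does not: a switch is permitted, not built in.

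The reply continues that any free-living single-arm study is open to dietary drift, that this is a pilot meant to inform a placebo-controlled trial, and that the diary should already show the vehicle. This stands as context. But the vehicle is part of the study instructions, so it can be fixed in a way that general diet cannot, and no use of the diary for this purpose is specified.

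On the recipe, a reader might infer that it breaks the study's limits outright. It is an example that permits other fruit, and plain water is always an option, so compliant versions exist. The low-proanthocyanidin foods could also be read as part of the allowed list. Even so, the recipe does not carry the daily limit over to a product taken twice a day. No figure in the documents shows that a second banana would threaten GP-SPI as the main source.

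On almond milk, the list bars almonds without mentioning almond products. It bars apples but permits limited apple juice, and where it means all products, as with berries, it says so. A conflict is therefore possible but not established.

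**Conclusion.** The concern holds as a gap in control, not as a demonstrated bias. The vehicle is free in both periods, nothing keeps it constant, and a net one-directional change at day 1 could not be separated from the effect of the grape polyphenols. The frequency and size of such a change are unknown. The false-positive figures above rest on assumed shifts and apply only to the taxon used for sizing; no document links banana or dairy to that taxon.

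The banana mismatch is firm under its stated condition, a banana smoothie for both daily packets: 2 servings against 1. The fruit line also reads as though banana were freely allowed. The status of almond milk needs a ruling from the study team.

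A reader might go further and infer that yogurt bacteria would appear directly in the 16S results. The documents do not say that the yogurt contains live cultures, and they restrict yogurt nowhere, so that inference is not supported and no change to the yogurt line follows.

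**What to change.** 1. In the run-in and GP-SPI paragraphs of section 1.3, have each participant choose one vehicle at day -5 and use it for every SPI and GP-SPI packet. Write the recipe for both products.
2. Reconcile the recipe with the food list: how a banana recipe used twice a day fits the one-serving rule, which list the fruit line refers to, and whether almond milk falls under the almond exclusion. The study team must settle these; the statistical requirement is only that the passages agree.
3. In section 6.1, add a sensitivity analysis of the primary outcome that excludes participants whose diary photographs show a change of vehicle after day 0. Define a change before the data are examined.

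**Cost.** Edits to the instructions and recipe sheet, and one further analysis of data already to be collected. Sample size and visits are unchanged. Participants have slightly less choice, which could affect palatability. If 10% to 40% still switched, the sensitivity analysis would keep about 14 to 22 of 24 completers (24 - 9.6 = 14.4; 24 - 2.4 = 21.6). The lower end is below the planned 16, so the analysis should support the main one, not replace it.

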b) Urine samples (100 µL aliquots) will be centrifuged (10,000 g for 10 min at 4 °C) to remove particulates followed by dilution with water (1:1 to 1:3 vol/vol). Samples (10 µl) will be added to 10 ml of ACN and centrifuged at 3000 g for 15 min. The supernatant will be collected, dried, reconstituted in 500 µl of ethanol (50 % v/v) containing 0.1 % ascorbic acid and (w/v) and transferred to HPLC vials for untargeted analyte detection by high resolution MS (20; 35).

To deplete common matrix interferences such as phospholipids, salts, and proteins and optimize sample preparation each sample supernatant produced in a) and b) may also be loaded to Oasis Prime HLB Cartridges (Waters). Sample preparation methods will be tested.

2) Chromatographic separation and high-resolution mass spectrometry (MS): Triplicates (i.e. technical replicates) of each serum or urine sample will be separated on a Dionex UltiMate 3000 Binary Rapid Separation UHPLC with Diode Array Detector with a reverse phase (RP) C18 column for retention of medium polar and non-polar analytes as well as a hydrophilic interaction chromatography (HILIC) column for retention of highly polar metabolites (35). Separation of samples on RP and HILIC columns prior to MS will provide more comprehensive metabolome coverage. To detect the greatest number of metabolites, gradient elution protocols will be optimized separately for serum and urine samples. Chromatographic separations will be followed by MS using a Thermo Scientific Q Exactive Plus Orbitrap high resolution mass spectrometer. The orbitrap provides high mass accuracy (1–2 p.p.m.), resolution up to 100,000 and dynamic range of 5,000. Data will be collected in both positive and negative ESI modes (mass range of 100–2,000 m/z).

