Quality control (QC): Three kinds of QC samples will be implemented: 1) A standard mixture solution of PAC-derived MM and/or bile acids at a concentration of 1 mg/L; 2) A bulk QC sample made by pooling equal aliquots of each urine or serum sample; 3) Bulk urine or serum QC sample spiked with standard mix. These QC controls will help evaluate retention time stability, peak shape, detector response and mass accuracy. To avoid freeze-thaws QC controls will be prepared, aliquoted, and stored at -80 °C. QC samples will be injected 5 times at the beginning of the run to ensure system equilibration, and then once every 10 samples to monitor stability of analysis. Samples will be randomized to reduce systematic error associated with measurement variability (35).

3) Data processing and metabolite identification: XCMS Online software (<https://xcmsonline.scripps.edu>) will be used to identify and line up MS peaks/metabolites. Background noise will be filtered. A 0.2 min retention time and 0.002 Da mass tolerance window will be applied. Metabolites will be identified using online databases such as Chemspider, METLIN, (<https://metlin.scripps.edu/index.php>), Human Metabolome Database (HMDB) (<http://www.hmdb.ca/>), MZedDB (<http://maltese.dbs.aber.ac.uk:8888/hrmet/index.html>) and Kyoto Encyclopaedia of Genes and Genomes (KEGG) (<http://www.genome.jp/kegg/>). Metabolite profile and identification will be achieved by comparing mass, RT, MS/MS fragmentation patterns in secondary LC-MS/MS analysis, and/or against standard compounds for aglycones. We will look for particular signatures of metabolites that are significantly increased in blood after GP intake (humans) or PAC intake (mice). As many metabolites are likely to be conjugated to glucuronide, sulphate and methyl groups, enzymatic treatments will be applied to release the aglycone for quantification purposes. After enzymatic treatment, samples will be profiled and compared to untreated samples. After deconjugation an increase in the signal of particular aglycones (previously quantified) is expected. The relative increase in these signals coupled with the decrease/disappearance of the conjugated compound will be used to quantify the concentration of these metabolites.

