6.0 Data Management Plan

6.1 Data Analysis

Statistical comparisons will focus on individual and aggregate comparisons with respect to baseline to follow-up change in gut microbiota populations and biochemistry profile in blood and urine samples.

For each outcome, the equality of the outcome means for GP-SPI versus SPI will be tested against a two-directional alternative, controlling the type 1 error at $\alpha = 0.05$. The analyses will be conducted using t-tests for between group analysis and with repeated measures to conduct analysis of variance. Post-hoc tests will be conducted for pairwise comparisons of GP-SPI and SPI employing the Tukey method for controlling the global comparison-wise significance at 0.05 level. Logarithms or other transformations will be applied for data seriously deviating from normality; alternatively, non-parametric analyses may be conducted.

Handling of missing data: The data will be analyzed using the procedures PROC MIXED and PROC GLIMMIX SAS (v 9.3 or later). Thus, mixed effects models for repeated measures will be employed to analyze all available data irrespective of missing or incomplete data attributable to dropouts or other phenomena. In anticipation of the possibility of missing data, we plan to conduct sensitivity analyses that compare our findings against protocol completer analyses and last observation carried forward analyses in addition to investigating characteristics of participants who fail to protocol.

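### Mass-spectrometry samples are randomised without keeping each participant's samples together, so within-person metabolite changes lose precision if the assay is run in more than one batch.

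*Combined protocol and SAP*

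**What the plan says.** The plan is in section 1.3, Metabolomics Workflow.

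- **Order of samples.** Under Quality control: "Samples will be randomized to reduce systematic error associated with measurement variability". No block, stratum or batch unit is named, and the number of batches is not given.
- **QC injections.** Among the QC materials is "A bulk QC sample made by pooling equal aliquots of each urine or serum sample". Five QC injections open the run so that the system can settle. After that, the stated frequency and aim are "once every 10 samples to monitor stability of analysis". The purpose is thus to evaluate and monitor. Correction of the data is not mentioned.
- **Replicates and columns.** The plan specifies "Triplicates (i.e. technical replicates) of each serum or urine sample" on two column types, reverse phase and HILIC, in both ionisation modes.
- **Analysis.** Item 4 (Statistical analysis) tests metabolites within subject across time-points, and also within and between groups. It names log transformation and Pareto scaling and leaves any further corrections to be chosen as the need arises. Section 6.1 says that the study focuses on "individual and aggregate comparisons with respect to baseline to follow-up change".
- **Samples.** Serum for metabolomics comes from days 0 and 11 only (section 1.8). Urine is collected on seven days (Table 1).

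**The concern.** The human study has one arm and a fixed sequence: SPI, a break day, then GP-SPI. Its main statistical strength is that each participant is their own control. An offset shared by all samples in a batch cancels from a within-person change when both samples are in that batch, and stays in the change when they are not. Randomising individual samples leaves that to chance.

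Metabolite changes in serum and urine are at stake, together with the co-inertia analysis that relates them to bacterial responders. Serum is the most exposed because each participant supplies a single pair, so no other time-point can offset a noisy one. How the samples were split cannot be changed after the run, and later correction may recover the lost precision only in part.

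**Working it through.** The plan states no power, batch count or batch variance for metabolomics, so there is no figure to reproduce. The calculation in section 1.5 concerns the relative abundance of *A. muciniphila* and does not bear on this assay.

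**Inputs from the documents.** 30 enrolled, 20% loss, hence 24 completers (section 4.3); 2 serum and 7 urine samples per person; 3 replicates; 2 columns; two-sided 0.05 (section 6.1).

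**Assumptions.** Equal batches, number B = 1, 2, 4 or 8. Batch variance as a fraction v of within-person variance: 0.25, 0.5 or 1. Triplicates injected together. 20 to 30 minutes per injection.

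**Step 1: is more than one batch plausible?** At N = 30, before QC:

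- Serum: 30 × 2 × 3 = 180 injections per column. At 20 to 30 minutes this takes 60 to 90 hours, or 2.5 to 3.75 days.
- Urine: 30 × 7 × 3 = 630 injections per column, which takes 210 to 315 hours, or about 9 to 13 days.
- Total: (180 + 630) × 2 columns = 1,620, doubled if the two polarities are run separately.

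Several batches are plausible for urine and less certain for serum. Serum preparation has many steps, so preparation sets could act as batches even inside one instrument run.

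**Step 2: how often is a pair split?** With M samples in B batches of m = M/B, the chance that two given samples fall in different batches is 1 − (m − 1)/(M − 1). For serum with 24 completers, M = 48:

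- B = 1: 0
- B = 2: 1 − 23/47 = 0.511
- B = 4: 1 − 11/47 = 0.766
- B = 8: 1 − 5/47 = 0.894

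For a urine pair (M = 168) the values are 0, 0.503, 0.754 and 0.880.

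**Step 3: variance of a change.** A pair in one batch has variance 2σw². A split pair has 2(σw² + σb²). Averaged over the allocation, the ratio to the one-batch case is 1 + P(split) × v, and the effective number of completers is 24 divided by that ratio.

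| Serum batches | v | Ratio | Rise in SE | 24 completers worth |
|---|---|---|---|---|
| 1 | any | 1.000 | none | 24 |
| 2 | 0.25 | 1.128 | 6% | 21.3 |
| 2 | 0.5 | 1.255 | 12% | 19.1 |
| 2 | 1 | 1.511 | 23% | 15.9 |
| 4 | 0.25 | 1.191 | 9% | 20.1 |
| 4 | 0.5 | 1.383 | 18% | 17.4 |
| 4 | 1 | 1.766 | 33% | 13.6 |

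**Step 4: the same in power.** Take a standardised serum change of 0.597, which 24 completers detect with 80% power when each pair shares a batch (paired t-test). Dividing that change by the square root of the ratio gives 75%, 71% and 63% power with two batches, and 73%, 66% and 56% with four, for v = 0.25, 0.5 and 1.

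**The case against.** The strongest reply is that the plan is silent on batching and that silence is not a decision. The text speaks of a single run, does not say that randomisation is unrestricted, and does not rule out keeping a participant together. Serum takes only a few days per column on the assumed timing, so one serum batch is quite possible, and then nothing is lost. This stands, and it makes the point conditional.

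Second, the plan has means of control: pooled, standard and spiked QCs, triplicates, an internal standard in serum, and room for further corrections. This stands in part. No batch or drift correction is named, the QC is there to monitor, and no internal standard is described for urine. Triplicates injected together do not average out an offset that they share. If replicates were spread over batches, the loss would be smaller than shown.

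Third, keeping participants whole moves batch offsets between people, which matters for PCA and PLS-DA on pooled samples. This is a real but small cost, because the human study has no parallel group whose comparison would suffer.

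A reader might also infer that every pair is affected, so that 24 completers fall to 24/1.25 = 19, 24/1.5 = 16 or 24/2 = 12. Those figures require every pair to be split. Random allocation splits about 51%, 77% or 89% of serum pairs with 2, 4 or 8 batches.

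**Conclusion.** The point holds as a conditional loss of precision. The plan randomises samples without a participant block and names no batch or drift correction, although it tests metabolites within subject. If a matrix and column is prepared or run in more than one batch and left uncorrected, the serum-pair precision of 24 completers falls to that of about 21, 19 or 16 with two batches, and 20, 17 or 14 with four. These figures rest on assumed variance ratios and batch counts, equal batches, and triplicates injected together. With one batch the loss is zero.

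Three wider readings are tempting and are not supported:

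- That all the within-person changes the trial relies on are affected. The primary endpoint uses 16S sequencing and safety uses the CMP, and neither passes through this assay. Among the stated endpoints, the samples for the microbiome-wide study are only to be collected and stored.
- That the time effect is biased. Random order protects against that.
- That DNA extraction plates and sequencing runs share the problem. The randomisation sentence belongs to the metabolomics quality control text and says nothing about them.

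**What to change.** State the preparation and run batches for each matrix and column. Then:

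1. Allocate participants at random to batches.
2. Keep all of a participant's samples of that matrix, with their replicates, in one preparation batch and one run batch.
3. Randomise order within participant. A shared batch does not remove drift inside the batch.
4. Pre-specify drift correction from the pooled QC injections already planned.
5. Include a batch term in analyses that compare or pool across people, and handle the batch offsets by that term or by the QC correction before PCA and PLS-DA.

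The cost is a different run list and a few lines of analysis plan. It is feasible because the pooled QC draws on every sample, which implies that the samples are in hand before the run starts. The one downside is that batch offsets then lie between people, which item 5 addresses.
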